8.4 Assessment of Pharmacokinetics

Plasma PK samples will be collected at time points specified in the PK sampling schedules provided in [Appendix 1](#) (Part A [SAD]) and [Appendix 2](#) (Part B [MAD]). In Part B (MAD), urine will also be collected as specified in [Appendix 2](#). Blood and urine sample collection, processing, and shipping details will be outlined in a separate lab manual or instructions.

Plasma and urine concentrations of ABI-4334 will be determined using a validated assay at a contracted bioanalytical laboratory. Plasma and urine concentrations of any potential ABI-4334 metabolites may also be determined. Furthermore, blood and urine samples will be stored for potential future bioanalytical testing of the parent drug or any metabolites and to support the validity of the study.

8.5 Unscheduled Visit Procedures

An Unscheduled Visit may be performed at any time at the discretion of the Investigator in order to further evaluate a subject. The specific assessments to be performed at these visits would be determined by the Investigator according to the nature of the subject-specific follow-up required. Suggested assessments, as applicable, are indicated in [Appendix 3](#).

Assessments performed should be documented in the subject's source documentation. Refer to [Section 8.3.5](#) for clinical laboratory assessments.

8.6 Premature Study Termination Visit Procedures

Should a subject prematurely discontinue from the study ([Section 7.1.2](#)), a Premature Study Termination Visit should be scheduled, as feasible. While the Investigator may include additional assessments and evaluations determined by the status of the individual subject, at a minimum, the assessments indicated in [Appendix 3](#) should be performed as soon as feasibly possible.

9 ADVERSE EVENTS AND TOXICITY MANAGEMENT

9.1 Definition of Adverse Event

An AE is any untoward medical occurrence in a study subject administered a study drug regardless of the causal relationship with treatment.

An AE, therefore, can be any unfavorable and unintended sign, symptom, or disease temporally associated with participation in an investigational study, whether or not considered study drug related. In addition to new events, any increase in the severity or frequency of a pre-existing condition that occurs after the subject signs the ICF for participation is considered an adverse event. This includes any side effect, injury, toxicity, or sensitivity reaction. AEs may also include complications associated with protocol mandated procedures.

An AE does not include the following:

- Medical or surgical procedures such as surgery, endoscopy, tooth extraction, and transfusion. The condition that led to the procedure may be an AE and must be reported
- Pre-existing diseases, conditions, or clinically significant laboratory abnormalities present or detected before the screening visit that do not worsen during the study
- Situations where an untoward medical occurrence has not occurred (eg, hospitalization for elective surgery, social and/or convenience admissions)
- Overdose without clinical sequelae
- Any medical condition or clinically significant laboratory abnormality with an onset date before the consent form is signed and not related to a protocol-associated procedure is not an AE. It is considered to be pre-existing and should be documented on the medical history CRF

9.2 Documenting Adverse Events

Adverse events will be monitored and recorded from the written informed consent obtained through end of study (completion of follow-up period or “lost to follow-up”). The Investigator will ask the subject at each visit if they have experienced any untoward effects since the last study visit. All AEs will be entered in the electronic case report forms (eCRFs); refer to the eCRF Completion Guidelines for additional information.

For the follow-up period for AEs, see [Section 9.5](#). For the definition of TEAEs, see [Section 10.4.4](#).

9.3 Assessment of Intensity

The severity of each AE is to be assessed by the Investigator according to the modified Division of AIDS (DAIDS) Table for Grading the Severity of Adult and Pediatric AEs ([Appendix 4](#)), which grades the severity of clinical AEs and laboratory abnormalities in a 4-category system.

For AEs not included in [Appendix 4](#), the following guidelines will be used to describe severity:

- Grade 1 (Mild): Mild symptoms causing no or minimal interference with usual social and functional activities with intervention not indicated
- Grade 2 (Moderate): Moderate symptoms causing greater than minimal interference with usual social & functional activities with intervention indicated
- Grade 3 (Severe): Severe symptoms causing inability to perform usual social and functional activities with intervention or hospitalization indicated (Of note, the term “severe” does not necessarily equate to “serious”)
- Grade 4 (Life-Threatening): Potentially life-threatening symptoms causing inability to perform basic self-care functions with intervention indicated to prevent permanent impairment, persistent disability, or death

9.4 Assessment of Causality

All AEs must have their relationship to study intervention assessed by the clinician who examines and evaluates the subject based on temporal relationship and his/her clinical judgment. Each AE must be recorded in the source documentation, whether serious or not serious. For the purposes of this study, each event is to be assessed with regard to the following causality categorizations, in the Investigator’s considered judgment:

- Not related: An AE with sufficient evidence to accept that there was no causal relationship to administration of study drug (eg, no temporal relationship because the study drug was administered after the onset of the event, an investigation showed that study drug was not administered, another cause was proven)
- Related: An AE occurred in a plausible time relationship to administration of study drug and that could not be explained by a concurrent disease or other drugs or events. The response to withdrawal of the drug (dechallenge) was clinically reasonable

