4.3 Duration of Treatment

The duration of treatment for each part of the study is provided below:

- Part A (SAD): 1 day
- Part B (MAD): 8 days

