7.2 Criteria for Discontinuation of Study Treatment for a Cohort

Study enrollment and drug administration in the current cohort will be stopped pending a full safety review for any the following:

- Any SAE considered as at least possibly related to study drug by the Investigator and/or the Sponsor's Medical Monitor
- Any Grade 4 AE considered as at least possibly related to the study drug by the Investigator and/or the Sponsor's Medical Monitor
- Two Grade 3 AEs that are similar in nature and considered as at least possibly related to the study drug by the Investigator and/or the Sponsor's Medical Monitor
- A pattern of significant symptoms, physical findings, or confirmed laboratory abnormalities (AEs) that, although individually minor, collectively represent a safety concern in the opinion of the Investigator and/or the Sponsor's Medical Monitor and are judged to be at least possibly related to study drug

If any of the above predefined criteria are met, the Sponsor will rapidly inform the study sites that the study drug should not be administered to additional subjects at the same or higher doses until the safety concern is reviewed and considered resolved by the DRC and the Investigator. A cohort with lower dose might be considered subsequently to continue to explore the study objectives.

If the study is stopped or suspended for reasons of safety, the Sponsor will notify the relevant regulatory agencies.

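### Protocol 9.4's two causality categories leave out a well-timed event with an unproven other cause, so the 9.10.2 stop and the related-TEAE tables have no rule for it

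*Combined protocol and SAP*

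**What the plan says.** **The scale.** Protocol 9.4 requires that "each event is to be assessed with regard to the following causality categorizations", in the Investigator's judgement, and gives two categories.

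- *Not related* is "An AE with sufficient evidence to accept that there was no causal relationship to administration of study drug". The examples include dosing after onset and another cause having been proven.
- *Related* requires a plausible time relationship and an event "that could not be explained by a concurrent disease or other drugs or events". A further sentence in the same definition reads "The response to withdrawal of the drug (dechallenge) was clinically reasonable".

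Protocol 4.3 gives the treatment duration as "Part A (SAD): 1 day" and 8 days for Part B.

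**Where causality is used.**

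- Protocol 9.10.2: after a Grade 3 or 4 AE the drug may continue if the event is unrelated and should be discontinued if it is related.
- SAP 5.1.3: an AE is related if the investigator ticked that box. A blank is also counted as related in the summaries.
- Protocol 7.1.2: subjects withdrawn for a drug-related AE are not replaced.
- Protocol 7.2: enrolment and dosing in a cohort stop on any of four criteria. Three are "Any SAE considered as at least possibly related to study drug by the Investigator", "Any Grade 4 AE considered as at least possibly related to the study drug by the Investigator" and "Two Grade 3 AEs that are similar in nature and considered as at least possibly related to the study drug". The fourth is a pattern of individually minor findings. All four use the *at least possibly related* threshold, and the Sponsor's Medical Monitor may make the call as well as, or instead of, the Investigator.

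**The concern.** A two-category scale works only if every event belongs in one of them. Here one definition asks for evidence against causation and the other asks for the absence of any competing explanation. The event in between is common in volunteer studies: a headache, nausea or raised ALT at a plausible time, with another possible cause that nobody has proven. The Investigator must tick a box whose definition the event does not meet, or leave it blank.

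A Grade 3 or 4 event of this kind in a subject still being dosed is neither clearly a reason to stop nor clearly a reason to continue under 9.10.2. The same facts can also appear in, or be absent from, the related-TEAE tables depending on the box chosen. In a first-in-human trial the default for a possibly drug-related event should be explicit and should lean towards caution.

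**Working it through.** The documents give no figure on this point to reproduce, so the check compares the sections.

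**1. Do the definitions cover every event?** Take an event with plausible timing:

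| Other facts | Meets *Not related*? | Meets *Related*? |
|---|---|---|
| Other cause proven | Yes | No |
| No other explanation, reasonable response to withdrawal | No | Yes |
| Other cause possible, not proven | No | No |
| No other explanation, response to withdrawal not assessable | No | No, read literally |

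Rows 3 and 4 have no category, and neither the protocol nor the SAP assigns them to one.

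**2. Where does the withdrawal condition fail?** Planned maximum numbers are 5 × 8 + 6 = 46 in Part A and 2 × 8 = 16 in Part B, 62 in all.

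- *Part A.* 46/62 = 74.2% is an upper figure for subjects with no continuing treatment to withdraw. Up to 8 subjects return for Cohort A6 and the 6 in Cohort A7 cross over, each with a second dose at least 7 days later that could be withheld. If Cohorts A1 to A5 fill, subjects with only one dose number from 40 − 8 = 32 (all of one cohort return) to 40 (none return).
- *Part B.* 9.10.2 calls for a stop once an event is related, but 9.4 makes the response to stopping part of being related. Section 9.10 mentions dose interruption, but 9.10.2 does not provide for one before the causality call.

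**3. What follows from the box?**

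- *9.10.2* matters only where a dose remains: the 16 Part B subjects, plus Cohort A6 or A7 subjects before their second dose.
- *SAP 5.1.3* follows the tick. An in-between event counts as related if *Related* is ticked or the field is blank, and does not count if *Not related* is ticked. In a 6:2 cohort one such subject moves the proportion from 0/6 to 1/6 = 16.7 points on active, or from 0/2 to 1/2 = 50 points on placebo. This is simply the weight of one subject.

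**4. How far does this reach the 7.2 halt?** Section 7.2 does not cite 9.4 or the CRF box. In plain words, a well-timed event with an unproven other cause is possibly related, so 7.2 already covers it. Section 10.6.2 adds a DRC assessment with no relatedness condition:

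| 7.2 criterion | Covered by 10.6.2? |
|---|---|
| SAE | Yes |
| Grade 4 AE | Yes |
| Two similar Grade 3 AEs | Only if 2 or more subjects are affected |
| Pattern of minor findings | No |

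What remains is that the 7.2 threshold has no counterpart on the only causality scale the protocol defines.

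**The case against.** The strongest reply is that the safety system does not depend on the 9.4 box. The 7.2 call is a separate judgement with a lower threshold, open to two parties. The DRC is unblinded and must assess SAEs, Grade 4 AEs and similar Grade 3 AEs in two or more subjects whatever their cause, and it may end a cohort early. Sentinel subjects in Cohorts A1 to A5 are observed for at least 3 days before the rest are dosed. Section 7.1.1 lets the Investigator stop a subject for an AE that is not tolerated. No inference is planned, and all TEAEs are tabulated and all AEs listed regardless of cause. Resolution as a single dose clears is a natural reading of the withdrawal sentence.

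Much of this stands. A reader might infer that the halting rules cannot work, or fire far less often than intended. If the halt followed the box, with an assumed 10% risk per subject in 6 active subjects and half of the events ticked *Not related*, the chance that a one-event rule fires would fall from 1 − 0.90^6 = 0.469 to 1 − 0.95^6 = 0.265. The documents give neither the risk nor the share, and they do not tie the halt to the box, so these figures do not measure an effect of this plan.

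The reply does not close the gap in 9.4. Discretion to stop a subject is not a rule for when to stop, a DRC assessment is not the 9.10.2 stop, and the natural reading of withdrawal is not written down.

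**Conclusion.** The point holds for 9.4 and what depends on it directly. The two categories are not exhaustive, and the withdrawal condition is unworkable after one dose and circular in Part B. If the strict *Related* definition is applied as written, possibly drug-related Grade 3 or 4 events escape the 9.10.2 stop and possibly related events drop out of the related-TEAE tables.

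The reach is limited: chiefly 16 planned Part B subjects, plus any second dose in Cohort A6 or A7, and descriptive tables in which one subject is one sixth of an active arm. The AE and laboratory components of the primary endpoint do not use relatedness; the treatment-discontinuation component can be affected through 9.10.2. The effect on the 7.2 halt is indirect, and the documents do not support a claim that the halt fails.

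This assumes that no rule exists elsewhere. The eCRF Completion Guidelines and the DRC charter are cited but not included, and either might address it. Even so, a definition that governs stopping belongs in the protocol, and the wording should be changed.

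**What to change.** In 9.4, define *Related* as any AE that does not meet *Not related*, and drop the withdrawal condition; improvement after stopping or clearance may be noted as supporting evidence. Add one sentence that *Related* means at least possibly related in 7.2. Section 9.10.2 and SAP 5.1.3 then follow without rewording. Optionally, state in 10.6.2 that any event meeting a 7.2 criterion is also a potential safety concern, which closes the pattern and single-subject Grade 3 gaps.

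No visits, samples or subjects are added. Some events with an unproven other cause may pause dosing until reviewed, and more AEs will be tabulated as related. In Part B, a Grade 3 or 4 event of this kind would stop that subject's drug. If an active subject is then withdrawn from the study for it, 7.1.2 bars replacement and the cohort could finish with 5 rather than 6 on active. Making *Related* the default is partly a policy choice. A team that does not want it could add a *possibly related* category instead, and say how 7.2, 9.10.2 and the SAP treat it.

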9.5 Adverse Event Follow-up

The Investigator is responsible to follow all AEs should through resolution, unless the event is considered by the Investigator to be unlikely to resolve due to the subject’s underlying disease, or the subject is lost to follow-up.

9.6 Serious Adverse Events

9.6.1 Definition of Serious Adverse Event

An SAE is any event that meets any of the following criteria:

- Death
- Life-threatening
- Inpatient hospitalization or prolongation of existing hospitalization
- Persistent or significant disability/incapacity
- Congenital anomaly/birth defect in the offspring of a subject
- Other: Important medical events that may not result in death, be life-threatening, or require hospitalization, may be considered an SAE when, based upon appropriate medical judgment, they may jeopardize the subject and may require medical or surgical intervention to prevent 1 of the outcomes listed in this definition. Examples of such events are:
 - Intensive treatment in an emergency room or at home for allergic bronchospasm
 - Blood dyscrasias or convulsions that do not result in inpatient hospitalization
 - Development of drug dependency or drug abuse

9.6.2 Definition of Terms

- Life threatening: An AE is life-threatening if the subject was at immediate risk of death from the event as it occurred; ie, it does not include a reaction that if it had occurred in a more serious form might have caused death. For example, drug-induced hepatitis that resolved without evidence of hepatic failure would not be considered life threatening even though drug induced hepatitis can be fatal
- Hospitalization: AEs requiring hospitalization should be considered SAEs. Hospitalization for elective surgery or routine clinical procedures that are not the result of AEs (eg, elective surgery for a pre-existing condition that has not worsened) need not be considered AEs or SAEs. If anything untoward is reported during the procedure, that occurrence must be reported as an AE, either “serious” or “non-serious” according to the usual criteria
- In general, hospitalization signifies that the subject has been detained (usually involving at least an overnight stay) at the hospital for observation and/or treatment that would not have been appropriate in the physician's office or outpatient setting. When in doubt as to whether “hospitalization” occurred or was necessary, the AE should be considered serious

- Disability/incapacitating: An AE is incapacitating or disabling if the experience results in a substantial and/or permanent disruption of the subject's ability to carry out normal life functions

9.6.3 Reporting Serious Adverse Events

All SAEs must be reported by the investigational staff within 24 hours of learning about the event using the SAE Report form to the Sponsor or its designee (eg, CRO Pharmacovigilance group).

The initial report should be promptly followed by detailed, written reports, which will include copies of relevant hospital case reports, autopsy reports, and other documents when requested and applicable.

For a follow-up report to the authorities, the monitor may be required to collect further information for a final evaluation of the case. Reporting to the respective country Health Authorities will be the responsibility of the Sponsor and the CRO.

The CRO will be responsible for informing all central Institutional Review Boards (IRBs)/Independent Ethics Committees (IECs) of SAEs as required. It will be the responsibility of the individual Investigators to inform any local IRBs/IECs of SAEs as required. Correspondence with the IRB(s)/IEC(s) relating to the reporting of SAEs will be retained in the study file.

9.7 Laboratory Abnormalities and Other Abnormal Assessments as AEs or SAEs

Laboratory abnormalities (defined as outside of reference range) are usually not recorded as AEs or SAEs, unless they are clinically significant (see definition of AEs in [Section 9.1](#)), as determined by the Investigator. Clinical laboratory abnormalities that require medical or surgical intervention or lead to study drug interruption or discontinuation must be recorded as an AE or SAE, if applicable. The modified DAIDS Table for Grading the Severity of Adult and Pediatric AEs ([Appendix 4](#)) will be used to assess the severity of laboratory abnormalities. In addition, laboratory or other abnormal assessments (eg, ECG and vital signs) that are associated with signs and/or symptoms must be recorded as an AE or SAE if they meet the definition of an AE or SAE described in [Sections 9.1](#) and [9.6](#). If the laboratory abnormality or abnormal assessment is part of a syndrome or diagnosis, record the syndrome or diagnosis (eg, anemia), not the laboratory result (ie, decreased hemoglobin).

9.8 Overdose

An overdose is defined as the accidental or intentional administration of any dose of a product which is above the maximum recommended dose as per protocol or in the product labelling (as it applies to the daily dose of the subject in question). The Medical Monitor may be contacted for questions concerning potential cases of overdose. An overdose is not in and of itself considered to be an AE unless it results in untoward medical effects. Any AE associated with an overdose or incorrect administration of study drug should be entered in the subject's source documentation and

Adverse Event eCRF. If the associated AE fulfills the criteria of an SAE, then the event should be reported to the Sponsor or CRO within 24 hours after the site learns of the event.

9.9 Pregnancy

9.9.1 Female Subjects Who Become Pregnant

The Investigator will collect pregnancy information on any female subject who becomes pregnant while participating in this study (see [Appendix 5](#) for contraceptive requirements). The initial information will be recorded on the Pregnancy Reporting form and submitted to the Sponsor or its designee within 24 hours of learning of a subject's pregnancy.

The subject will be followed to determine the outcome of the pregnancy. The Investigator will collect follow-up information on the subject and the neonate and the information will be forwarded to the Sponsor or its designee. Generally, follow-up will not be required for longer than 6 to 8 weeks beyond the estimated delivery date. Any termination of pregnancy will be reported, regardless of fetal status (presence or absence of anomalies) or indication for the procedure.

While pregnancy itself is not considered to be an AE or SAE, any pregnancy complication or elective termination of a pregnancy for medical reasons will be reported as an AE or SAE. A spontaneous abortion (occurring at < 22 weeks gestational age) or still birth (occurring at > 22 weeks gestational age) is always considered to be an SAE and will be reported as such.

Any female subject who becomes pregnant while participating in the study will discontinue the study drug(s) immediately.

9.9.2 Male Subjects With Partners Who Become Pregnant

The Investigator will attempt to collect pregnancy information on any male subject's female partner who becomes pregnant while the male subject is participating in this study (see [Appendix 5](#) for contraceptive requirements).

After obtaining the necessary signed informed consent from the pregnant female partner directly, the Investigator will record pregnancy information on the Pregnancy Reporting form and submit it to the Sponsor or its designee within 24 hours of learning of the partner's pregnancy. The female partner will also be followed to determine the outcome of the pregnancy. Information on the status of the mother and child will be forwarded to the Sponsor. Generally, the follow-up will be no longer than 6 to 8 weeks following the estimated delivery date. Any termination of the pregnancy will be reported regardless of fetal status (presence or absence of anomalies) or indication for the procedure.

